2022-04-14

**FACE TO FACE OR DIGITALLY? A COMPARISON OF FIRST-LINE INTERVENTIONS DELIVERY FOR
PEOPLE WITH HIP OR KNEE OSTEOARTHRITIS (NCT04836988)**

Background

Osteoarthritis (OA) is among the leading causes of disability worldwide and due to its raising prevalence, the identification of appropriate care and care delivery modalities is a priority for the health care systems [1, 2]. Exercise and education constitute the first-line intervention for people with knee and hip OA and have been shown to be effective regardless of symptoms and disease severity [3, 4]. Unfortunately, there is a discrepancy between recommended treatment and what patients receive. Less than 40% of people with OA seeking care seem to receive recommended first line management internationally [5]. To implement those guidelines, the Better Management of Patients with OsteoArthritis (BOA), a face-to-face concept including education and an option to exercise, has been developed and are offered at primary care clinics in Sweden since 2008 [6]. However, traditional face to face interventions present barriers, such as limited access and lack of flexibility, which may limit the patients' adherence with the interventions [7]. Digital delivery of the management program may be one way of overcoming such barriers [8, 9]. In light of the current Covid-19 pandemic, digitally delivered treatments may gain even further awareness as a feasible treatment option. Both delivery methods have been reported to reduce OA symptoms in patients with hip and/or knee OA [10, 11], but little is known whether the results of digital interventions are comparable with traditional face-to-face rehabilitation programs.

Aim

To compare the outcomes (average treatment effect) of two different modalities of first-line treatment delivery (face-to-face vs. digitally) after 3 months of program participation.

Hypothesis

There will be no difference in the average treatment effect of the main outcome between the two delivery methods.

Methods

This is a retrospective observational registry-based study comparing outcomes of a face-to-face and a digital OA management program.

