Three months of first-line OA treatment delivered either face-to-face or digitally with a program adherence of 80% or higher. The choice of this cut-off was based on recommendations in the Swedish Guidelines for management of knee and hip osteoarthritis by the National Board of

Health and Welfare. Adherence defined as $\geq 80\%$ completed education videos, exercises and questionnaires offered in the digital program and participation in two out of three educational lessons and at least 10 of the 12 supervised group exercise sessions offered in the BOA program.

Main outcome

Main outcome will be self-reported change in pain on the NRS-scale between baseline and three months follow-up. The NRS comprises an 11-point scale where 0 indicates no pain and 10 indicates the worst possible pain [13] (Table 1).

Secondary outcomes

Secondary outcomes will be change in self-reported walking difficulties (dichotomous reply, yes/no), willingness for joint surgery (dichotomous reply, yes/no) and health-related quality of life, assessed with the EuroQol – 5 dimension descriptive system (EQ-5D-3L)[14] between baseline and three months follow-up (Table 1).

Sample size

As this study aims at estimating treatment effects, the important issue to assess is not power (related to a hypothesis), but precision – i.e. the width of the confidence interval. To illustrate this, consider the example of an RCT to compare mean joint pain after exercise intervention for OA, between persons that receive the treatment in different modalities. The minimum clinically important difference is typically considered one unit on a 0-10 NRS scale. To obtain a 95% confidence interval for the between-group difference with a width of at most 0.5 units (i.e. very precise) in a sample with a typical standard deviation of 1.5, with 99% probability, we will need ~ 630 patients in total. Considering our cohort size of >2000 persons who underwent the intervention, we will be able to estimate between-group differences also in subgroups, by sex, BMI, etc.

Statistical analysis

In this study we will use observational data to emulate an equivalence trial comparing the effect on joint pain of a digitally delivered first-line intervention and of an in-person delivered first line intervention for people with OA of the hip or knee.

Main outcome analysis

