The main outcome will be analyzed using a propensity score matching approach [17]. We will estimate the propensity score using a logistic regression model, in which we will regress the treatment status on the observed baseline characteristics of the participants. The characteristics to include in the propensity score will be selected using the disjunctive cause

criteria [16], including factors in the analysis identified as causes of treatment allocation(exposure) and/or the pain change (outcome) (Table 2). We will use nearest neighbor matching to select controls (BOA participants) whose propensity score is closest to that of the treated subject. Furthermore, we will use an optimal matching strategy to minimize the total within-pair difference of the propensity score. Within-pair differences in main outcome will be analysed using a paired t-test. Finally, we will adjust the analysis for baseline pain using linear regression in order to increase the precision of the estimates and minimize the regression to the mean effect [17, 18].

Assessing propensity score balance

Balance of baseline variables between treated and control subjects in the matched study population will be assessed using standardized difference [19].

Equivalence bounds

In order to establish equivalence between the interventions the pain change after the intervention should differ of less than 1-point on a 0-10 NRS pain scale. This cut off was selected based on previous work identifying 1-point change as the MCID in people with OA [20].

Sensitivity analysis

In order to evaluate and contrast the influence of choice of analysis method on study results, linear regression analysis based on the same adjustment set used for the propensity score, representing the causal effect studied, will be applied and both adjusted and unadjusted estimates will be presented, discussed and contrasted against results from the propensity score matched analysis.

Missing data

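### The 1-point equivalence bound is tied to no confidence interval, so as worded it can be met by the estimate alone

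*SAP*

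**What the plan says.** The elements that bear on the equivalence conclusion sit in five sections of the SAP:

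- **Statistical analysis:** "In this study we will use observational data to emulate an equivalence trial" of the two delivery modes, with joint pain as the outcome.
- **Equivalence bounds:** to establish equivalence, "the pain change after the intervention should differ of less than 1-point on a 0-10 NRS pain scale". The section justifies the value 1 as the MCID. It names no interval, confidence level, test or deciding analysis.
- **Hypothesis:** "There will be no difference in the average treatment effect of the main outcome between the two delivery methods".
- **Main outcome analysis:** "Within-pair differences in main outcome will be analysed using a paired t-test", with no null value given. Then: "Finally, we will adjust the analysis for baseline pain using linear regression".
- **Sample size:** "the important issue to assess is not power (related to a hypothesis), but precision". A 95% interval appears here only: "To obtain a 95% confidence interval for the between-group difference with a width of at most 0.5 units". It is a width target in an illustrative RCT, and nothing requires that interval to lie within ±1.

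**The concern.** An equivalence conclusion needs a rule that takes account of sampling error. The usual rule is that the whole confidence interval lies inside the bounds, or the matching pair of one-sided tests. The SAP gives the bound without that rule. An absolute estimate just under 1 would be equivalent if the bound is applied to the estimate, and not shown to be equivalent if it is applied to the 95% interval. The choice is left open until after the data are seen. On the estimate reading, nothing controls the chance of declaring equivalence when the true difference is at or just beyond the margin.

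The other elements do not repair this. A hypothesis of no difference is not a hypothesis of a difference smaller than 1 point, and a t-test against zero does not address equivalence. Those two elements can even point the opposite way from the bound. It is also only implied, not stated, that the baseline-adjusted matched estimate is the one to be compared with the bound.

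**Working it through.** **Inputs.** From the SAP: margin 1 point (Equivalence bounds); SD 1.5, 95% interval of full width at most 0.5 with 99% probability, about 630 patients in total, and a cohort of more than 2000 (Sample size); 1:1 matching (Data extractions and linkages). Assumed here: the SD of 1.5, given for mean joint pain in the illustration, also applies to pain change; within-pair correlation ρ = 0; normal approximation.

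**The SAP's own figure.** Find the smallest n per arm for which t(0.975, 2n−2) · s · √(2/n) ≤ 0.25 with probability at least 0.99, where (2n−2)s²/1.5² is chi-square on 2n−2 degrees of freedom. This gives 316 per arm, 632 in total, so the stated figure of about 630 is reproduced. Without the 99% assurance, 2 × (1.96 × 1.5/0.25)² = 276.6, that is 277 per arm and 554 in total.

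**Sample sizes used.** The SAP states "Considering our cohort size of >2000 persons who underwent the intervention" but not whether this is both groups or one. I therefore use 315 pairs (half of 630), 1000 pairs (2000 split evenly) and 2000 pairs (2000 in the digital group alone).

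**Formulas.**

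- SE = SD × √(2(1−ρ)/n). For 315 pairs: 1.5 × √(2/315) = 0.1195.
- Largest absolute estimate that passes an interval rule = 1 − z × SE. For 315 pairs at 95%: 1 − 1.96 × 0.1195 = 0.766.
- Probability that the estimate rule declares equivalence at true difference δ near 1: Φ((1−δ)/SE).
- Probability that the 95% interval rule does so: Φ((1−δ)/SE − 1.96).

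**Results, SD 1.5, ρ = 0.**

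| Quantity | 315 pairs | 1000 pairs | 2000 pairs |
|---|---|---|---|
| SE | 0.120 | 0.067 | 0.047 |
| Largest absolute estimate passing, 95% interval | 0.77 | 0.87 | 0.91 |
| Largest absolute estimate passing, 90% interval | 0.80 | 0.89 | 0.92 |
| Estimate rule, δ = 1.0 | 50% | 50% | 50% |
| 95% interval rule, δ = 1.0 | 2.5% | 2.5% | 2.5% |
| Estimate rule, δ = 1.05 | 34% | 23% | 15% |
| 95% interval rule, δ = 1.05 | 0.9% | 0.3% | 0.1% |
| Estimate rule, δ = 1.1 | 20% | 7% | 2% |
| 95% interval rule, δ = 1.1 | 0.3% | 0.03% | 0.002% |

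**Range.**

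- SD 2.5 (assumed): the two readings disagree from 0.61 / 0.78 / 0.85 up to 1.00, and the estimate rule at δ = 1.1 gives 31% / 19% / 10%.
- SD 1.5 with ρ = 0.3 (assumed): they disagree from 0.80 / 0.89 / 0.92 up to 1.00, and the estimate rule at δ = 1.1 gives 16% / 4% / 0.6%.
- Subgroups, which the SAP says it can estimate: with an assumed 100 pairs and SD 1.5, SE = 0.212 and the 95% limit is 1 − 1.96 × 0.212 = 0.58.

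**Conflict with the no-difference hypothesis.** A two-sided 5% test against zero rejects when the absolute estimate exceeds 1.96 × SE = 0.23 / 0.13 / 0.09. Between those values and 0.77 / 0.87 / 0.91, that test finds a difference while even the strict interval rule finds equivalence. The SAP does not say which prevails.

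**The case against.** The strongest reply is that the interval reading is the natural one. The SAP speaks of bounds and of an emulated equivalence trial, and it puts precision ahead of power. It also mentions the 1-unit MCID immediately before planning a 95% interval. The criterion could be read as describing the true difference, with inference left to that interval. No sentence says that the bound is applied to a point estimate. This stands as far as it goes: an interval reading is a fair inference. It is still not written, and even that reading leaves the confidence level and the deciding analysis open.

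A second reply is that a paired t procedure also yields a confidence interval, and that two one-sided paired t-tests would be a valid equivalence test. That is correct, but the SAP specifies neither use.

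A third reply is that little is at stake. The 315-pair figures belong to an illustration, and at 1000 or 2000 pairs the readings differ only in a narrow band. The 50% figure at the margin would hold for any estimate rule in any study. Nothing in the SAP suggests a true difference near 1 point. All of this is accepted. It limits the likely effect on the conclusion but does not supply the missing rule.

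**Conclusion.** The concern holds. The criterion on which the main conclusion rests can, as worded, be met by a point estimate, and no other part of the SAP ties it to an interval. With SD 1.5 and uncorrelated pairs, the verdict depends on the reading for absolute estimates above about 0.87 (1000 pairs) or 0.91 (2000 pairs), and above 0.77 at the illustrative 315 pairs. A larger SD widens that zone; positive within-pair correlation narrows it. For estimates well inside the bound the conclusion does not change. It should be fixed because the decision rule ought to be settled before the data are seen, rather than because a different conclusion is likely.

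**What to change.** Restate the hypothesis as an absolute difference in mean NRS pain change of less than 1 point, and add to Equivalence bounds:

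> Equivalence is concluded only if the whole two-sided 95% CI for the baseline-pain-adjusted mean difference in NRS pain change in the matched sample lies within −1 to +1. If multiple-imputation regression replaces matching, the same rule applies to its pooled estimate. A t-test of zero difference does not decide equivalence.

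The 95% level is proposed because it is the only one in the SAP. A 90% interval (two one-sided tests at 5%) is also defensible; with SD 1.5 that choice changes the verdict only for absolute estimates of about 0.77–0.80 / 0.87–0.89 / 0.91–0.92 (315 / 1000 / 2000 pairs). Separately, the Missing data section gives the same 5% threshold for both of its branches and needs its own correction; the wording above does not depend on it.

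The cost is wording only, with no new data. The rule is stricter than one on the estimate. With SD 1.5, the 95% interval rule concludes equivalence with these probabilities:

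| True difference | 315 pairs | 1000 pairs | 2000 pairs |
|---|---|---|---|
| 0.5 | 98.7% | about 100% | about 100% |
| 0.7 | 71% | 99.4% | about 100% |
| 0.8 | 39% | 85% | 98.8% |

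For comparison, the estimate rule at 0.8 with 315 pairs gives Φ(0.2/0.1195) = 95%, so at that size the loss is substantial for true differences close to the margin. With SD 2.5 (assumed) the interval rule gives 71% / 99.4% / about 100% at 0.5 and 32% / 77% / 97% at 0.7.

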The study was approved by the regional ethics committee of the Swedish Ethical Review Authority (Dnr 2019-06288, decision date 2020-02-11 and is pre-registered at ClinicalTrials.gov (NCT04836988). Participants were informed that data generated from the register may be used for research purposes at registration (BOA) or provided digital informed consent for the same purpose at registration (JA). The study adheres to the STROBE guidelines for observational studies.

Data sources

BOA (face-to-face): The BOA registry was started in 2008 and currently includes more than 100,000 individuals with OA who have registered for an evidence-based self-management program, including education, exercise and weigh management if needed at a primary care clinic.

Joint Academy (digital program): The digital self-management program started in 2014 and was originally inspired by the Swedish evidence based face-to-face BOA self-management treatment program [9]. The associated registry currently includes more than 30 000 individuals with OA. The intervention consists of a digital OA self-management program (Joint Academy®) [11, 12] comprising text lectures on OA with accompanying quizzes, physical activity and self-management in OA. The participant also receives exercises aiming at improving strength and neuromuscular control of various levels based on each individuals' progression in the program.

Data extractions and linkages

All data extracted from the digital self-management program (JA) and BOA registries. Criteria for inclusion in the data extraction are:

- Clinical diagnosis of OA, with knee or hip OA as their index (most symptomatic) joint
- Enrolled in either of the two programs between April 1, 2018 and December 31, 2019
- Provided 3-month follow-up data for the main outcome on or before March 31, 2020
- Program adherence of 80% or higher.

The data from the two registers will be linked using personal identity numbers to identify individuals that may have participated in both programs during the specific time window. Patients that participated in both programs will be excluded from further analysis.

The JA participants will be matched 1:1 to participants in the BOA register using the propensity scoring approach described below.

Main exposures and outcomes

Exposures

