Data on study drop-outs will be summarized by treatment group using frequency counts to assess any imbalance. If the fraction of missing study data is non-ignorable (i.e. 5% or more with missing data in either outcome and/or any adjustment variable), then multiple imputation techniques, such as MICE [21] will be applied to the analysis of the primary outcome. The analysis method will also be altered to a linear regression approach, as opposed to that of propensity score matching, in order to facilitate incorporation of missing data methods in the analysis procedure. However, when the fraction of missing data is small (i.e. 5% or more with missing data in either outcome and/or any adjustment variable), the primary analysis will be performed using a complete case approach.

References

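### The missing-data rule prints the same trigger, 5% or more, for two different primary analyses, and leaves the unit of the 5% open

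*SAP*

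**What the plan says.** The Main outcome analysis section of the SAP sets the default: "The main outcome will be analyzed using a propensity score matching approach". The Missing data section then gives two branches.

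- **Imputation branch.** The trigger is "If the fraction of missing study data is non-ignorable (i.e. 5% or more with missing data in either outcome and/or any adjustment variable". Multiple imputation is then applied to the primary outcome, and the estimator changes: "The analysis method will also be altered to a linear regression approach, as opposed to that of propensity score matching".
- **Complete-case branch.** The trigger is "However, when the fraction of missing data is small (i.e. 5% or more with missing data in either outcome and/or any adjustment variable". In that case "the primary analysis will be performed using a complete case approach".

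Two inclusion criteria under Data extractions and linkages limit where values can be missing: "Provided 3-month follow-up data for the main outcome on or before March 31, 2020" and "Clinical diagnosis of OA, with knee or hip OA as their index (most symptomatic) joint".

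**The concern.** The rule selects both the missing-data method and the primary estimator. Imputation with regression and complete-case matching cannot both be the primary analysis, yet the condition printed for each is the same. Read literally, a data set with 5% or more missing satisfies both. A data set below 5% satisfies neither: it falls back on matching as the default, with no instruction for incomplete records.

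Correcting the percentage leaves a further question. The trigger does not say whether the 5% is the proportion of patients with a gap anywhere in the outcome or adjustment set, or the proportion missing in any one variable. The same data set can lie below 5% on one count and above it on the other.

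This is a retrospective registry study. The SAP is dated April 2022 and the follow-up window closed in March 2020. A rule that picks the primary estimator for data already collected should need no interpretation. The SAP itself treats the choice of method as something that could influence results, since its Sensitivity analysis section plans to contrast matching with regression.

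**Working it through.** **Step 1: the two triggers side by side (Missing data section)**

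| | Imputation branch | Complete-case branch |
|---|---|---|
| Label for the missing fraction | non-ignorable | small |
| Printed threshold | 5% or more | 5% or more |
| Scope | outcome and/or any adjustment variable | the same |
| Primary analysis | multiple imputation, linear regression | complete cases; by default propensity score matching |

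At 5% or more both columns apply. Below 5% neither does. No other section of the SAP resolves this.

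**Step 2: where values can be missing**

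The 3-month main-outcome value is required for inclusion, so pain change can be missing only through baseline pain. The rule therefore works almost wholly through the baseline variables. Table 1 marks 15 variables as used for matching, and baseline pain is one of them. The most affected joint is complete by the inclusion criterion, which leaves 15 − 1 = 14 that can be missing.

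**Step 3: does the unit of the 5% matter?**

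The SAP gives no missingness rates, so there is no figure of its own to reproduce here. What follows is an illustration under stated assumptions:

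- The adjustment set is the Table 1 matching variables. The Main outcome analysis section cites a Table 2, which is not in the text available.
- The missing rate m is the same in each of k variables.
- Missingness either overlaps fully (the same patients lack everything) or is independent across variables.

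Fraction of records with at least one gap:

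- full overlap: m
- independence: 1 − (1 − m)^k

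With m = 1%:

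- per variable: 1%, below the trigger
- per record, full overlap: 1%, below the trigger
- per record, independence, k = 14: 1 − 0.99^14 = 13.1%, above the trigger
- per record, independence, k = 15 (if the index joint could also be missing): 1 − 0.99^15 = 14.0%

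Per-variable rate at which the per-record fraction reaches 5% under independence:

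- k = 14: 1 − 0.95^(1/14) = 0.37%
- k = 15: 1 − 0.95^(1/15) = 0.34%

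So under independence and equal rates, with the second trigger corrected to less than 5%, any per-variable rate from 0.37% to just under 5% gives complete-case matching on the per-variable reading and imputation with regression on the per-record reading. Under full overlap the two readings never differ.

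**Step 4: scale of the threshold**

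The Sample size section refers to "Considering our cohort size of >2000 persons who underwent the intervention". On the per-record reading, 5% of 2000 is 0.05 × 2000 = 100 records, so the switch comes at 100 or more incomplete records.

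**The case against.** The strongest reply is that the duplicated percentage corrects itself. The sentence opens with a contrast and calls the fraction small, so only less than 5% makes sense, and no analyst would choose complete cases because missingness is large. That is right about intent. It does not repair the text of a rule that selects the primary estimator.

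On the unit, the grammar leans towards counting patients: a percentage with missing data in the outcome or any adjustment variable reads most naturally as a union over variables. This stands. The point is an ambiguity, not a contradiction, and would not justify a finding alone.

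The numbers in Step 3 rest on assumed rates, and independence is unfavourable, because blank baseline items may well cluster in the same patients. This also stands. The figures show that the readings can part, not that they will, and they say nothing about the effect on the estimate.

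It can also be said that, once the percentage is corrected, the complete-case branch plainly returns to matching, and that the planned regression sensitivity analysis would report both estimators there. Both remarks are fair for that branch. Neither covers the imputation branch, where the SAP replaces matching with regression.

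**Conclusion.** The concern holds. The threshold for the complete-case branch is wrong as written: it repeats the condition for imputation with regression, so the plan assigns two primary analyses to the same data. That conclusion rests on the text alone and needs no assumption.

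The unit of the 5% is a secondary gap that should be closed in the same edit. Its practical size is unknown. At an assumed 1% missing in each of 14 variables, the per-record fraction lies between 1% under full overlap and 13.1% under independence, against a trigger of 5%.

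This should be fixed. It is most likely a wording slip, but it sits in the line that chooses the primary estimator.

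**What to change.** 1. In the second trigger of the Missing data section, replace the printed threshold with *less than 5%*.
2. In both triggers, state the unit: either the percentage of records with a missing value in the outcome or any adjustment variable, or the percentage missing in any single variable. Use the same unit in both.
3. State that the complete-case branch is the propensity score matched analysis described under Main outcome analysis.

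The cost is a few phrases of SAP wording, with no change to design or data.

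Optionally, and not because the SAP is in error on this, the imputation branch could also report the matched result, for example by matching within each imputed data set and pooling. That would keep the contrast between methods planned under Sensitivity analysis, for modest extra programming.
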